## VIII. SIGNIFICANCE

Severe RSV bronchiolitis is a major risk factor for subsequent wheezing episodes and eventually asthma. Previous interventions in the setting of severe RSV bronchiolitis targeted allergic (i.e. eosinophilic) inflammation and were found to be ineffective in preventing subsequent wheezing episodes. We will use an innovative intervention (azithromycin) that is safe for use in children, is capable of attenuating neutrophilic inflammation, and has the mechanistic rationale to be an effective intervention.

This trial may identify the first effective intervention to apply during severe RSV bronchiolitis with the goal of preventing post-RSV RW, and ultimately asthma. A meaningful reduction in post-RSV RW would have significant impact on society and the health system through reductions in morbidity and health care utilization. This trial will be conducted by a multidisciplinary team, including experts in asthma/RSV clinical trials, infectious diseases, and microbiome research. Understanding the pathways through which the azithromycin modifies the microbiome, and how these changes relate to the development of RW, may inform the development of additional microbiome-directed therapies for asthma prevention.

## **X. APPENDIX 1.**

### COMBINED LIST OF DRUGS THAT PROLONG QT AND/OR CAUSE TORSADES DE POINTES (TDP)

CredibleMeds® has reviewed available evidence for the drugs on this list and concluded that they either 1) have a Known Risk of TdP ⚠️ 2) prolong the QT interval and therefore have a Possible Risk of TdP ❓ or 3) have a Conditional Risk of TdP ⚠️, that is, under certain conditions such as overdose, drug - drug interactions or when administered to certain high-risk individuals (e.g. congenital long QT syndrome).

Generic Name	Brand Name
Alfuzosin	Uroxatral®
Amantadine	Symmetrel® and others
Amiodarone	Cordarone® and others
Amisulpride	Solian® and others
Amitriptyline	Elavil® (Discontinued 6/13) and others
Anagrelide	Agrylin® and others
Apomorphine	Apokyn® and others
Aripiprazole	Abilify® and others
Arsenic trioxide	Trisenox®
Arteminol+piperazine	Eurartesim®
Asenapine	Saphris® and others
Astemizole	Hismanal®
Atazanavir	Reyataz®
Atomoxetine	Strattera®
Azithromycin	Zithromax® and others
Bedaquiline	Sirturo®
Bepidil	Vascor®
Bortezomib	Velcade® and others
Bosutinib	Bosulif®
Buprenorphine	Butrans® and others
Capecitabine	Xeloda®
Ceritinib	Zykadia®
Chloral hydrate	Aquachloral® and others
Chloroquine	Aralen®
Chlorpromazine	Thorazine® and others
Cilostazol	Pletal®
Ciprofloxacin	Cipro® and others
Cisapride	Propulsid®
Citalopram	Celexa® and others
Clarithromycin	Biaxin® and others

Generic Name	Brand Name
Clomipramine	Anafranil®
Clozapine	Clozaril® and others
Cocaine	Cocaine
Crizotinib	Xalkori®
Cyamemazine (cyamemazine)	Tercian®
Dabrafenib	Tafinlar®
Dasatinib	Sprycel®
Degarelix	Firmagon®
Delamanid	Delyba®
Desipramine	Pertofrane® and others
Dexmedetomidine	Precedex® and others
Diphenhydramine	Benadryl® and others
Disopyramide	Norpace®
Dofetilide	Tikosyn®
Dolasetron	Anzemet®
Domperidone	Motilium® and others
Donepezil	Aricept®
Doxepin	Sinequan® and others
Dronedarone	Multaq®
Droperidol	Inapsine® and others
Eribulin mesylate	Halaven®
Erythromycin	E.E.S.® and others
Escitalopram	Ciprallex® and others
Ezogabine (Retigabine)	Potiga® and others
Famotidine	Pepcid® and others
Felbamate	Felbatol®
Fingolimod	Gilenya®
Flecainide	Tambocor® and others
Fluconazole	Diflucan® and others
Fluoxetine	Prozac® and others

Generic Name	Brand Name
Foscarnet	Foscavir®
Furosemide (frusemide)	Lasix® and others
Galantamine	Reminyl® and others
Gatifloxacin	Tequin®
Gemifloxacin	Factive®
Granisetron	Kytril® and others
Grepafloxacin	Raxar®
Halofantrine	Halfan®
Haloperidol	Haldol® (US & UK) and others
Hydrochlorothiazide	Apo-Hydro® and others
Hydrocodone - ER	Hysinglaä,ç ER and others
Hydroxychloroquine	Plaquenil® and others
Hydroxyzine	Atarax® and others
Ibutilide	Corvert®
Iloperidone	Fanapt® and others
Imipramine (mepipramine)	Tofranil®
Indapamide	Lozol® and others
Isradipine	Dynaciro®
Itraconazole	Sporanox® and others
Ivabradine	Procoralan® and others
Ketoconazole	Nizoral® and others
Lapatinib	Tykerb® and others
Lenvatinib	Lenvima®
Leuprolide	Lupron® and others
Levofloxacin	Levaquin® and others
Levomethadyl	Orlaam®
Lithium	Eskalith® and others
Loperamide	Imodium® and many other OTC and Rx brands
Mesoridazine	Serentil®

Generic Name	Brand Name
Methadone	Dolophine® and others
Metoclopramide	Reglan® and others
Metronidazole	Flagyl® and many others
Mifepristone	Korlym® and others
Mirabegron	Myrbetriq®
Mirtazapine	Remeron
Moexipril/HCTZ	Uniretic® and others
Moxifloxacin	Avelox® and others
Nelfinavir	Viracept®
Nicardipine	Cardene®
Nilotinib	Tasigna®
Norfloxacin	Noroxin® and others
Nortriptyline	Pamelor® and others
Ofloxacin	Floxin®
Olanzapine	Zyprexa® and others
Ondansetron	Zofran® and others
Osimertinib	Tagrisso®
Oxaliplatin	Eloxatin®
Oxytocin	Pitocin® and others
Paliperidone	Invega® and others
Panobinostat	Farydak®
Pantoprazole	Protonix® and others
Papaverine HCl	none
Paroxetine	Paxil® and others
Pasireotide	Signifor®

Generic Name	Brand Name
Pazopanib	Votrient®
Pentamidine	Pentam®
Perflutren lipid microspheres	Definity®
Pimozide	Orap®
Pipamperone	Dipiperon (E.U) and others
Posaconazole	Noxafil® and others
Probucol	Lorelco®
Procainamide	Pronestyl® and others
Promethazine	Phenergan®
Propofol	Diprivan® and others
Quetiapine	Seroquel®
Quinidine	Quinaglute® and others
Quinine sulfate	Qualaquin®
Ranolazine	Ranexa® and others
Rilpivirine	Edurant® and others
Risperidone	Risperdal®
Ritonavir	Norvir®
Roxithromycin	Rulide® and others
Saquinavir	Invirase®(combo)
Sertindole	Serdolect® and others
Sertraline	Zoloft® and others
Sevoflurane	Ulane® and others
Soifenacin	VESicare®
Sorafenib	Nexavar®
Sotalol	Betapace® and others

Generic Name	Brand Name
Sparfloxacin	Zagam®
Sulpiride	Dogmatil® and others
Sunitinib	Sutent®
Tacrolimus	Prograf® and others
Tamoxifen	Nolvadex®(discontinued 6/13) and others
Telaprevir	Incivo®
Telavancin	Vibativ®
Telithromycin	Ketek®
Terfenadine	Seldane®
Tetrabenazine	Nitomax® and others
Thioridazine	Mellaril® and others
Tizanidine	Zanaflex® and others
Tolterodine	Detrol® and others
Toremifene	Fareston®
Torsemide	Demadex® and others
Trazodone	Desyrel® (discontinued 6/13) and others
Trimipramine	Surmontil® and others
Tropisetron	Navoban® and others
Vandetanib	Caprelsa®
Vardenafil	Levitra®
Vemurafenib	Zelboraf®
Venlafaxine	Effexor® and others
Voriconazole	VFend®
Vorinostat	Zolinza®
Ziprasidone	Geodon® and others

**Note:** Medicines on this list are reviewed on an ongoing basis to assure that the available evidence supports their continued placement on this list. Because, the list changes regularly, we recommend always checking the website at [crediblemeds.org](https://www.crediblemeds.org) for the most up-to-date information. Most drugs have multiple brand names and it is not practical to list them on this form. The [CredibleMeds.org](https://www.crediblemeds.org) website provides a partial list of the more common brands.

**Disclaimer and Waiver:** The information presented here is intended solely for the purpose of providing general information about health-related matters. It is not intended for any other purpose, including but not limited to medical advice and/or treatment, nor is it intended to substitute for the users' relationships with their own health care providers. To that extent, by use of this list and the information it contains, the user affirms the understanding of the purpose and releases AZCERT, Inc. from any claims arising out of his/her use of this list. The Terms of Use Agreement for this list and the [CredibleMeds website](https://www.crediblemeds.org/terms) is available at <https://www.crediblemeds.org/terms>. The absence of drugs from these lists should not be considered an indication that they are free of risk of QT prolongation or torsades de pointes. Few medicines have been tested for this risk in patients, especially those with congenital long QT syndrome. This list and the [CredibleMeds® website](https://www.crediblemeds.org) are intended for personal and professional use only and are protected by U.S. Copyright (title 17, U.S. Code). Unauthorized commercial use is prohibited.

Generated: June 8, 2016. List last revised: May 31, 2016

## XI. APPENDIX 2.

### SARS-COV-2 MEASUREMENT TESTING:

#### Background: The APW-RSV II clinical trial

The APW-RSV II clinical trial is investigating if the addition of azithromycin to routine bronchiolitis care, among infants hospitalized with RSV bronchiolitis, reduces the occurrence of recurrent wheeze during the preschool years.

We recruited 200 participants during 3 consecutive RSV seasons. Study participants were randomized to receive azithromycin or placebo for 2 weeks. The treatment phase for the last participant ended in spring 2019 and study follow-up will continue until fall 2020, and thus the final year of observation will include the COVID-19 pandemic.

#### COVID-19 and its potential implications on the APW-RSV II clinical trial

COVID-19, caused by the novel coronavirus, SARS-CoV-2, started in China in late 2019 and became a global pandemic affected millions worldwide. On April 6, the CDC COVID-19 Response Team reported that occurrence of clinical COVID-19 was lower in children than in adults (<https://www.cdc.gov/mmwr/volumes/69/wr/mm6914e4.htm>). However, a very recent report from China (<https://doi.org/10.1101/2020.03.03.20028423>) revealed that among contacts of subjects infected with SARS-CoV-2, the infection rate was similar between children and adults. The difference between these 2 reports may be related to the high rate of asymptomatic SARS-CoV-2 infections among children: estimated as up to 28% of young infected children. However, children have not been targeted for testing in the United States, and thus the rate of both symptomatic and asymptomatic infection remains unknown.

Given these uncertainties in terms of the prevalence and severity of this infection in young children, it is plausible to suggest that COVID-19 infection has the potential to impact the outcomes of the APW-RSV II clinical trial. The primary outcome of the APW-RSV II clinical trial is: *“The occurrence of a third episode of post-RSV wheezing measured over a follow up duration of 18-48 months, quantified by a Cox proportional hazards regression model, and compared between the groups.”*

In addition, almost all secondary outcomes of the APW-RSV II clinical trial may be affected by COVID-19. These include:

- g. Time to physician asthma diagnosis.
- h. Time to asthma diagnosis OR to the third episode of wheezing.
- i. Annualized number of days with: any respiratory symptoms (wheezing, cough, or shortness of breath), or albuterol use.

- j. Rate of oral corticosteroid courses use.
- k. Rate of antibiotic courses use.

In the APW-RSV clinical trial we are looking for the development of recurrent wheezing/asthma in children who have already demonstrated susceptibility to respiratory viral infections, as all were hospitalized due to RSV bronchiolitis. It is unknown if these children are more likely to be infected with SARS-CoV-2 and what will be the impact of COVID -19 on short and long-term respiratory symptoms in these children. As COVID-19 infection has the potential to affect the clinical trial outcomes, understanding the rate of its occurrence is essential in evaluating this exposure on our outcomes of interest.

#### Methods: SARS-CoV-2 measurements

In order to determine the prevalence of SARS-CoV2 infection in the study cohort, we will assess SARS-CoV-2 infection status as demonstrated by presence of SARS-CoV2 antibody (IgG and IgM) in peripheral blood. This approach was selected instead of direct viral detection using nasopharyngeal swabs for the following reasons:

1. Most importantly, antibody testing will give us valuable information on past infection while a PCR based test can only provide information on the current infection status (one point in time).
2. Antibody testing conducted by a blood test is safer for the research team and family as it is not associated with virus transmission risk, as opposed to the small risk associated with obtaining a nasal swab.

We plan to utilize the COVID 19 IgG serology test of the LabCorp lab and not a research lab kit, in order to increase the reliability and the validity of the test and to allow us to share the results with participant families.

After obtaining IRB approval, we will approach the caregivers of study participants (currently 190 participants are retained) and will request their consent for SARS-CoV-2 serology testing. SARS-CoV-2 testing will be voluntary; unwillingness to provide consent will not affect continued participation in the APW-RSV II clinical trial. It is anticipated that parents will likely agree to participate as knowing the SARS-Cov-2 status of their children will be valuable for them.

The test will be obtained at the last study clinic visit that will be conducted late summer-fall 2020. If clinic visit will not be able to be conducted due to Washington University COVID 19 regulations, we will send the participants to a LabCorp lab to obtain the test.

#### Methods: Primary outcome

The primary outcome of the APW-RSV clinical trial will remain the same (the occurrence of a third episode of post-RSV wheezing); however, the primary outcome assessment will include the SARS-Cov-2 infection status as an additional exposure covariate.

#### Methods: Exploratory outcome

Wheezing rates among our study populations 6-months before and 6-months after SARS-Cov-2 activity started in the St. Louis area (March 2020).

#### Methods: Analysis plan

In order to evaluate the effect of the exposure (SARS-Cov-2 infection) we will conduct a sensitivity analysis to assess whether SARS-Cov-2 infection status of the study participants is associated with primary outcome of the APW-RSV II clinical trial (recurrent wheeze). We will include infection status as a time-dependent covariate in our Cox regression model. As it is not possible to determine the exact date of infection for study participants, for those participants testing positive for SARS-Cov-2 we will assume an infection date of March 1, 2020. We will compare the results of this more complex model with our original pre-specified model, and if the results are not appreciably different then we will retain the original model as the primary analysis and the model including infection status will be included as a supplement.

We will also employ sensitivity analyses that include infection status for the secondary outcomes.

In addition, we will conduct exploratory analyses that will entail: (1) estimates of the proportion of participants infected with SARS-Cov-2 overall and stratified by treatment arm, and (2) for SARS-CoV-2 positive participants, a comparison of the wheezing rates in the 6-months prior to the SARS-Cov-2 activity in the St. Louis area (September 2019 to February 2020) to the wheezing rates 6-months after activity in the region (March 2020 to September 2020). For the analysis of wheezing rates, we will test the statistical null hypothesis of no difference in wheezing rates for SARS-Cov-2 positive participants in pre vs. post SARS-Cov-2 activity in St. Louis using a generalized linear model assuming a Poisson or negative binomial regression distribution. If we reject the null hypothesis ( $P < 0.05$ ) and the wheezing rates are elevated in the post-outbreak period then we will conclude that wheezing rates were higher in the post-outbreak period for participants that tested positive for SARS-Cov-2.

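### The exploratory before/after COVID wheeze comparison uses seropositive children only and sets autumn-winter against spring-summer, so it cannot separate infection from season, ageing or pandemic-period changes

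*Combined protocol and SAP*

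**What the plan says.** Appendix 2 describes the comparison in two places.

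- **Methods: Exploratory outcome** defines it as "Wheezing rates among our study populations 6-months before and 6-months after SARS-Cov-2 activity started in the St. Louis area", with activity dated from March 2020. It is not restricted by serostatus.
- **Methods: Analysis plan** restricts it: "for SARS-CoV-2 positive participants, a comparison of the wheezing rates in the 6-months prior to the SARS-Cov-2 activity". The before window is "September 2019 to February 2020" and the after window is "the wheezing rates 6-months after activity in the region (March 2020 to September 2020". The null hypothesis is "no difference in wheezing rates for SARS-Cov-2 positive participants in pre vs. post SARS-Cov-2 activity in St. Louis", tested "using a generalized linear model assuming a Poisson or negative binomial regression distribution". If P < 0.05 and the later rate is the higher one, "then we will conclude that wheezing rates were higher in the post-outbreak period for participants that tested positive for SARS-Cov-2".

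The plan states no seronegative comparison group for this analysis, no season or age term, no person-time offset and no handling of repeated observations on a child. A separate Cox sensitivity analysis enters infection status as a time-dependent covariate, with all infections dated 1 March 2020.

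**The concern.** Within seropositive children, period is the only contrast, and several things change with it: virus season, six months or so of ageing, pandemic-related changes in contact with other children, and infection itself. With no group that shares the first three but not the last, the model has nothing with which to separate them.

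Two smaller points add to this. The windows appear to differ in length although both carry the same label. The outcome definition and the analysis plan also name different populations, so two analysts could produce two different results, each defensible from the text.

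What is at stake is how one exploratory result will be read. Appendix 2 introduces serology because infection might affect the trial's outcomes. A test with a P < 0.05 rule in infected children will be taken as evidence about infection, whichever way it falls.

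**Working it through.** **1. Window lengths.** The plan labels both windows six months. Calendar counts give:

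| Convention | Before | After | Ratio |
|---|---|---|---|
| First and last months both included | 6 months, 182 days | 7 months, 214 days | 214/182 = 1.18 |
| Start of first month to start of last month | 5 months, 153 days | 6 months, 184 days | 184/153 = 1.20 |
| Last month included before, excluded after (to 1 September 2020) | 182 days | 184 days | 184/182 = 1.01 |

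Only the mixed convention reproduces six and six.

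**2. Season.** Section V.A gives the RSV season as usually November to April. Four of those months (November to February) fall in the before window and two (March, April) in the after window. This describes RSV admissions, not wheeze. The documents give no wheeze seasonality, so the ratios below are assumptions.

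With correct person-time, observed rate ratio = seasonal ratio × infection ratio. The infection ratio hidden as no change is 1 / seasonal ratio:

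- 0.8: 1/0.8 = 1.25
- 0.67: 1/0.67 = 1.49
- 0.5: 1/0.5 = 2.0

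**3. Effect on the decision rule.** Assume 20 expected episodes before, a true infection ratio of 2.0, a 214-day after window and a correct offset. Expected total = 20 + 20 × seasonal ratio × 2.0 × 1.18. The chance of a significant rise comes from a two-sided 0.05 Wald test of two Poisson rates, conditional on that total and counting upward rejections only:

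| Seasonal ratio | Total episodes | Chance of an elevated verdict |
|---|---|---|
| 1.0 | 67 | 75% |
| 0.67 | 52 | 15% |
| 0.5 | 44 | 2% |

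**4. Unequal windows if no offset were used.** With equal true rates and raw counts over 182 and 214 days, the chance of a false elevated verdict is:

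| Total episodes | Unequal windows | Equal windows |
|---|---|---|
| 10 | 1.8% | 1.0% |
| 20 | 4.6% | 2.1% |
| 40 | 5.9% | 1.9% |
| 80 | 11.8% | 2.8% |
| 160 | 16.9% | 2.4% |

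This runs opposite to the assumed seasonal effect and vanishes with an offset.

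**5. Ageing.** Section VII.B.1 gives a control-group monthly hazard of a third episode rising to about 5% at the end of year 1, then falling to 3% by the end of year 2, 2% in year 3 and 1% in year 4. First- and second-season recruits are past that peak throughout both windows. Third-season recruits (November 2018 to April 2019) reach month 12 between about November 2019 and April 2020, so for them the direction is unclear. This is a hazard of one event, not an episode rate. It shows that risk changes with time since admission, not by how much here.

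**6. What seronegative children add.** Suppose season and period act alike in both groups. At a seasonal ratio of 0.5 and an infection ratio of 2.0, the after/before ratio is 0.5 × 2.0 = 1.0 in positives and 0.5 in negatives. The ratio of the two is 1.0/0.5 = 2.0, which recovers the infection ratio.

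**7. Numbers available.** Methods: SARS-CoV-2 measurements gives 190 retained participants and no seroprevalence. At an assumed 2% to 20%, 4 to 38 children would be positive.

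**The case against.** The plan's conclusion is descriptive: it says rates were higher in a period among children who tested positive and names no cause. The analysis is labelled exploratory. All of that stands, and it keeps this a minor point.

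Four stronger readings are tempting, and the documents do not support them.

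- **That the rule would probably report no increase, or could never show an effect.** The plan defines no conclusion for a non-significant result. The size of wheeze seasonality is not given, and step 3 shows how far the answer depends on it. If the after window really is the low season, a rise seen in spite of that would be informative.
- **That the longer after window biases the result by 18%.** This requires modelling counts without an offset. The plan speaks of rates throughout, which makes that unlikely, and ending on 1 September removes the difference. What remains is unstated detail.
- **That Appendix 2 has no comparison with uninfected children.** The Cox sensitivity analysis has one, and the plan extends infection-status sensitivity analyses to the secondary outcomes.
- **That a seronegative comparison is free.** Testing is voluntary, so serostatus will exist only for children whose caregivers consent. The interaction is also less precise than the within-positive change.

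The population mismatch could be read as a short outcome label followed by its fuller specification. That is fair, but the two still differ and one line would settle it.

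**Conclusion.** The concern holds in a limited form. The comparison as specified cannot attribute a change in wheezing, or the lack of one, to SARS-CoV-2 infection, because period carries season, ageing and pandemic-period exposure with it and no seronegative children are included. This follows from the design and needs no assumed figure. The size does need one: seasonal ratios of 0.8 to 0.5 would hide infection ratios of about 1.25 to 2.0.

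The window lengths (182 and 214 days counted inclusively) and the two population definitions are inconsistencies of wording. The first matters to the result only if person-time is ignored. The randomised treatment comparison and the Cox sensitivity analysis are not affected. Low priority, but inexpensive to put right.

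**What to change.** In Appendix 2, Methods: Analysis plan:

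1. Fit the Poisson or negative binomial model in all children with a serology result, with terms for period, serostatus and their interaction.
2. State a log person-time offset and a method for within-child correlation (for example GEE or a child random effect).
3. Use equal windows: 1 September 2019 to 29 February 2020 and 1 March to 31 August 2020 (182 and 184 days).
4. Base any statement about infection on the interaction, and keep the within-positive change as a descriptive result.
5. Align the population in Methods: Exploratory outcome with the analysis plan.

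The cost is a few lines of analysis text. All 190 retained families are to be approached for testing, and wheeze is already recorded for every child at calls and visits, so no new data collection is needed.

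Some limits remain. The two seronegative cells add to the variance of the interaction, and both estimates will be imprecise if few children are positive. Serostatus is known only for consenting children. The interaction assumes that season and restrictions acted alike in both serogroups. Infection dates are unknown, and testing is in late summer to fall 2020, so the after window will include some pre-infection time and dilute any effect. The report should state these limits.

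### The exploratory before/after wheeze test in Appendix 2 takes two counts from each seropositive child but names a Poisson or negative binomial GLM with no child term, so its standard error can be too large or too small

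*Combined protocol and SAP*

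**What the plan says.** In Appendix 2, Methods: Analysis plan, the test is introduced as exploratory ("In addition, we will conduct exploratory analyses that will entail"). It is defined as follows.

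- **Children and contrast:** "for SARS-CoV-2 positive participants, a comparison of the wheezing rates in the 6-months prior to the SARS-Cov-2 activity in the St. Louis area" against the period after. The same children therefore supply both counts.
- **Windows:** "September 2019 to February 2020) to the wheezing rates 6-months after activity in the region (March 2020 to September 2020".
- **Null hypothesis:** "no difference in wheezing rates for SARS-Cov-2 positive participants in pre vs. post SARS-Cov-2 activity in St. Louis".
- **Model:** "using a generalized linear model assuming a Poisson or negative binomial regression distribution". Nothing further is said about the model.
- **Conclusion rule:** if P is below 0.05 "and the wheezing rates are elevated in the post-outbreak period", the plan will conclude that rates were higher after the outbreak began.

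In section VII.A, under secondary and exploratory outcomes analyses, six-month rates of antibiotic use, systemic corticosteroid use and upper respiratory infection are treated as repeated measures and compared by GEE. Appendix 2 neither repeats that nor refers to it.

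**The concern.** Two counts from one child are likely to be correlated, because some children wheeze more than others in any period. An ordinary GLM has no place for that correlation. The two distributions the plan allows also respond differently to variation between children: the negative binomial model charges all of it to error, and the Poisson model charges none of it. With no child term and no rule for choosing, the same data could pass or fail the 0.05 rule depending on which distribution is fitted.

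The stake is modest but concrete. The plan attaches a stated conclusion to this P value, and the number of seropositive children may be small. Appendix 2 (Methods: SARS-CoV-2 measurements) gives 190 retained participants and no expected number positive.

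**Working it through.** The plan gives no sample size, rate, dispersion, standard error or power for this test, so there is no figure of its own to reproduce. From the plan come the paired data, the two candidate models and the 0.05 level, taken as two-sided because the sidedness is not stated. Everything else below is assumed.

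**Set-up.** There are n children, a mean of r episodes per child per period, equal periods and no true change. Each count has variance r + k·r², where k is the total dispersion. The two counts of a child have covariance c·r², where c is the part of k that is stable within the child. The variance of the log rate ratio is then:

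- true: (2/n)(1/r + k − c)
- reported by a plain Poisson GLM: (2/n)(1/r)
- reported by an unpaired negative binomial GLM: (2/n)(1/r + k)

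The Poisson standard error is right only if k = c, and the negative binomial one only if c = 0. In between, one is too small and the other too large.

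**Case 1: stable differences only (k = c).** The Poisson standard error is correct. The negative binomial standard error is too large by sqrt(1 + r·k):

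| r | k | ratio |
|---|---|---|
| 0.25 | 0.5 | sqrt(1.125) = 1.06 |
| 0.5 | 1 | sqrt(1.5) = 1.22 |
| 1 | 1 | sqrt(2) = 1.41 |
| 1 | 2 | sqrt(3) = 1.73 |

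Take n = 20, r = 1, k = 1. The true and Poisson standard errors are sqrt(2/20) = 0.316, and the negative binomial one is sqrt(0.1 × 2) = 0.447. Now take a true rate ratio of 2 (log 0.693).

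- The true standard error is sqrt((1 + 1/2)/20) = 0.274. Power with the correct standard error is Φ(0.693/0.274 − 1.96) = 0.72.
- The negative binomial standard error is sqrt((1 + 1/2 + 2)/20) = 0.418. Its power is Φ((0.693 − 1.96 × 0.418)/0.274) = 0.32.

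Simulation with windows of six and seven months and an offset (2,000 null datasets) gave an empirical SD of 0.333. Poisson had a standard error of 0.317 and rejected 5.7%; negative binomial had 0.433 and rejected 1.1%. A separate simulation put power at 0.38 for the negative binomial model, against 0.71 for a child-clustered test with a small-sample t correction.

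**Case 2: stable plus period-specific variation.** Take a shared child variance of 1 and a period-specific variance of 0.5, acting multiplicatively. Then k = 2 × 1.5 − 1 = 2 and c = 1. For n = 20 and r = 1:

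- true standard error: sqrt(0.1 × 2) = 0.447
- Poisson: 0.316, so null rejection is 2(1 − Φ(1.96 × 0.316/0.447)) = 16.6%
- negative binomial: sqrt(0.1 × 3) = 0.548, which is too large

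Simulation gave an empirical SD of 0.452. Rejection was 15.1% for Poisson (14.6% in the separate simulation), 2.6% for negative binomial and 9.7% for a child-clustered standard error without a small-sample correction. With n = 40, simulated Poisson rejection was 10.2% at r = 0.5 and 17.4% at r = 1. Over all simulated n (10, 20, 40) and r (0.5, 1, 2) with this variance structure, Poisson ran from 5.2% to 25.2% and negative binomial from 1.5% to 3.8%.

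**Case 3: period-specific variation only (c = 0, k = 1, n = 20, r = 1).** The negative binomial standard error is about right (0.435 against an SD of 0.449; rejects 5.6%). Poisson rejects 15.3%. That error is overdispersion, not pairing.

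**Window length.** September to February is six calendar months. March to September is seven if September counts. Without a person-time offset, a constant rate would appear as a ratio of 7/6 = 1.17.

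**The case against.** The strongest objection is to a reading that a reader might well infer: that the plan ignores the pairing and that its standard error is therefore wrong. The documents do not support that. Appendix 2 is silent on pairing; it does not say that the counts are treated as independent. The plain Poisson standard error, one of the two options named, is correct when differences between children are stable. In that setting, with the same windows for every child, conditional (fixed-child) Poisson gives the same estimate and standard error, so it corrects nothing by itself. When wheeze also varies by period, it shares the Poisson shortfall.

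It can also be said that choosing between Poisson and negative binomial after looking at dispersion is ordinary practice. That does not help here. A dispersion check on the counts sees k but not c, so it would move the analyst to the negative binomial model even in Case 1, where Poisson is right.

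Other parts of the objection stand. The factor of 1.06 to 1.73 applies only to the negative binomial option and assumes perfectly stable child effects. Every rate, dispersion and sample size used is an assumption. Clustering without a small-sample correction would swap a conservative error for an anti-conservative one. The two windows also cover different seasons, which no standard error can repair. Finally, the rule leads only to a descriptive statement in an exploratory analysis.

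**Conclusion.** The point holds as a gap in specification with a measurable effect. The named model has no term for two counts per child, and neither distribution gives a valid standard error across the plausible variance structures. Under the assumed inputs, the negative binomial option is conservative when child effects are stable: at n = 20, a mean of one and a dispersion of one, power for a doubling of the rate falls from 0.72 to 0.32 in closed form. The Poisson option is sound in that case. It rejects roughly 10% to 17% of the time at a nominal 5% when period-specific variation is added at means of 0.5 to 1, for the examples with 20 or 40 children shown.

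The direction of the error therefore depends on which model is picked and on a variance structure the documents do not describe. A reader might also infer that the trial's main result is at risk. It is not: the primary Cox analysis and its separate infection-status sensitivity analysis do not use this test. The importance is low.

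**What to change.** In Appendix 2, replace the open choice of GLM with one pre-specified model: a Poisson GEE with period as the covariate and the child as the cluster, robust variance, a small-sample correction (for example a t reference with n − 1 degrees of freedom, n being the number of seropositive children), and an offset of log(person-time observed). State whether September 2020 is in the second window, and state that the test is two-sided if that is meant. Conditional Poisson should not be offered as a stand-alone alternative.

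The cost is a sentence or two and no new data. There are two statistical downsides. Power is slightly lower than with plain Poisson if there is no period-specific variation. Some inflation also remains with very few children, about 6% to 8% at a nominal 5% in the assumed scenarios, so the P value should be read with the number of seropositive children beside it.
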